*** Figures produced for DSMB**

Data Listings

Listing	Title	DSMB*
Listing 16.2.1.1	Study Completion/Discontinuation Details	
Listing 16.2.1.2	Eligibility/Randomization	
Listing 16.2.1.3	Exclusions from Per Protocol Population	
Listing 16.2.3.1	Subject General Information	X
Listing 16.2.3.2	Informed Consent	
Listing 16.2.4.1	Demographic Characteristics	X
Listing 16.2.4.2	Baseline Characteristics	X
Listing 16.2.4.3	Pre-injury Narrative – Baseline Status – Parts 1, 2 and 3	
Listing 16.2.4.4	Glasgow Coma Scale	
Listing 16.2.4.5	Medical History	
Listing 16.2.4.6	Prior, and Concomitant Medications	
Listing 16.2.4.7	Concomitant Procedures	
Listing 16.2.4.8	Surgical Therapy	
Listing 16.2.4.9	Study Admission	
Listing 16.2.4.10	Subject Transfer	
Listing 16.2.4.11	Facility Transfer	
Listing 16.2.4.12	Intubation	
Listing 16.2.4.13	Daily Fluid	
Listing 16.2.5.1	Study Drug Administration Parts 1 and 2	X
Listing 16.2.5.2	End of Treatment	X

Listing	Title	DSMB*
Listing 16.2.6.1.1	Glasgow Outcome Scale, Questions	X
Listing 16.2.6.1.2	Glasgow Outcome Scale, Explanation of Categories	X
Listing 16.2.6.1.3	Glasgow Outcome Scale – Extended, Explanation of Categories	
Listing 16.2.6.1.4	Glasgow Outcome Scale – Part 1	X
Listing 16.2.6.1.5	Glasgow Outcome Scale, Glasgow Outcome Scale-Extended Narrative – Parts 1-6	X
Listing 16.2.6.1.6	Primary Efficacy, Covariates, and Subgroup Variables (Observed Values)	X
Listing 16.2.6.1.7	Primary Efficacy, Covariates, and Subgroup Variables (Missing Values Imputed)	X
Listing 16.2.6.2	Sliding Dichotomy	
Listing 16.2.6.3	Mortality	X
Listing 16.2.6.4.1	SF-36, Explanation of Categories	
Listing 16.2.6.4.2	SF-36 (Individual Questions) - Parts 1, 2 and 3	
Listing 16.2.6.4.3	SF-36 (Scales and Summary Scores) - Parts 1 and 2	
Listing 16.2.6.5.1	CT Scan and Classification - Parts 1, 2 and 3	
Listing 16.2.6.5.2	CT Scan Comparison - Parts 1, 2 and 3	
Listing 16.2.6.6.1	Intracranial Pressure	
Listing 16.2.6.6.2	Intracranial Pressure Monitoring	
Listing 16.2.6.7	Cerebral Perfusion Pressure	
Listing 16.2.6.8.1	Therapy Intensity Level Parts 1 and 2	
Listing 16.2.7	Adverse Events	X
Listing 16.2.8.1.1	Laboratory (Coagulation) Results	
Listing 16.2.8.1.2	Laboratory (Hematology) Results	
Listing 16.2.8.1.3	Laboratory (Serum Chemistry) Results	
Listing 16.2.8.1.4	Laboratory (Urinalysis) Results	
Listing 16.2.8.1.5	Laboratory (Pregnancy Test) Results	
Listing 16.2.8.2	Vital Signs	X
Listing 16.2.8.3	Physical Examinations	
Listing 16.2.8.4	12-Lead Electrocardiogram (ECG) Parts 1 and 2	
Listing 16.2.8.5	Arterial Blood Gas	X
Listing 16.2.8.6	Neuroworsening Parts 1 and 2	

*** Listings produced for DSMB**

Note: Listings generated for all mITT subjects.

Statistical Output

Appendix	Title
Appendix 14.2.1.2	Analysis of Glasgow Outcome Scale at 6 Months Post Injury – Missing Values Imputed (mITT Population)* The above appendix will include the SAS output details relating to Table 14.2.1.2 and 14.2.1.3 (Analysis, ORs and CIs).
Appendix 14.2.1.5	Analysis of Glasgow Outcome Scale at 6 Months Post Injury – Observed Values (mITT Population) The above appendix will include the SAS output details relating to Table 14.2.1.5 and 14.2.1.6 (Analysis, ORs and CIs).
Appendix 14.2.1.8	Analysis of Glasgow Outcome Scale at 6 Months Post Injury – Observed Values (PP Population) The above appendix will include the SAS output details relating to Table 14.2.1.8 and 14.2.1.9 (Analysis, ORs and CIs).
Appendix 14.2.1.11	Analysis of Glasgow Outcome Scale at 6 Months Post Injury for US Only – Missing Values Imputed (mITT Population) The above appendix will include the SAS output details relating to Table 14.2.1.11 and 14.2.1.12 (Analysis, ORs and CIs).
Appendix 14.2.1.13	Analysis of Glasgow Outcome Scale at 6 Months Post Injury – Missing Values Imputed (Unadjusted Analysis) (mITT Population) The above appendix will include the SAS output details relating to Table 14.2.1.13 and 14.2.1.14 (Analysis, ORs and CIs).
Appendix 14.2.2.2	Summary and Analysis of Sliding Dichotomy at 6 Months Post Injury – Missing Values Imputed (mITT Population)
Appendix 14.2.2.5	Summary and Analysis of Sliding Dichotomy at 6 Months Post Injury – Observed Values (mITT Population)
Appendix 14.2.2.8	Summary and Analysis of Sliding Dichotomy at 6 Months Post Injury – Observed Values (PP Population)
Appendix 14.2.2.11	Summary and Analysis of Sliding Dichotomy at 6 Months Post Injury for US Only – Missing Values Imputed (mITT Population)
Appendix 14.2.3.2	Analysis of Dichotomized (GR, MD vs. SD, V/D) Glasgow Outcome Scale at 6 Months Post Injury – Missing Values Imputed (mITT Population) The above appendix will include the SAS output details relating to Table 14.2.3.2 and 14.2.3.3 (Analysis, ORs and CIs).
Appendix 14.2.3.5	Analysis of Dichotomized (GR, MD vs. SD, V/D) Glasgow Outcome Scale at 6 Months Post Injury – Observed Values (mITT Population) The above appendix will include the SAS output details relating to Table 14.2.3.5 and 14.2.3.6 (Analysis, ORs and CIs).
Appendix 14.2.3.8	Analysis of Dichotomized (GR, MD vs. SD, V/D) Glasgow Outcome Scale at 6 Months Post Injury – Observed Values (PP Population) The above appendix will include the SAS output details relating to Table 14.2.3.8 and 14.2.3.9 (Analysis, ORs and CIs).

Appendix	Title
Appendix 14.2.3.10	Analysis of Dichotomized (GR vs. MD, SD, V/D) Glasgow Outcome Scale at 6 Months Post Injury – Missing Values Imputed (mITT Population)
	The above appendix will include the SAS output details relating to Table 14.2.3.10 and 14.2.3.11 (Analysis, ORs and CIs).
Appendix 14.2.3.12	Analysis of Dichotomized (GR, MD, SD vs. V/D) Glasgow Outcome Scale at 6 Months Post Injury – Observed Values (mITT Population)
	The above appendix will include the SAS output details relating to Table 14.2.3.12 and 14.2.3.13 (Analysis, ORs and CIs).
Appendix 14.2.4.1	Analysis of Glasgow Outcome Scale at 6 Months Post Injury – Exploratory Analysis – Missing Values Imputed (mITT Population)
	The above appendix will include the SAS output details relating to Table 14.2.4.1 (Analysis, ORs and CIs).
Appendix 14.2.5.1	Summary and Analysis of Mortality at Month 6 (mITT Population)
Appendix 14.2.5.2	Summary and Analysis of Mortality at Month 1 (mITT Population)
Appendix 14.2.5.3	Summary and Analysis of Mortality at Month 6 (PP Population)
Appendix 14.2.5.4	Summary and Analysis of Mortality at Month 1 (PP Population)
Appendix 14.2.5.5	Summary and Kaplan-Meier Analysis of Time to Death (days) (mITT Population)
Appendix 14.2.5.6	Summary and Cox Proportional Hazards Analysis of Time to Death (days) (mITT Population)
Appendix 14.2.6.2	Analysis of Glasgow Outcome Scale at 3 months post injury – Observed Values (mITT Population)
	The above appendix will include the SAS output details relating to Table 14.2.6.2 and 14.2.6.3 (Analysis, ORs and CIs).
Appendix 14.2.7.2	Analysis of Glasgow Outcome Scale - Extended at 6 Months Post Injury – Observed Values (mITT Population)
	The above appendix will include the SAS output details relating to Table 14.2.7.2 and 14.2.7.3 (Analysis, ORs and CIs).
Appendix 14.2.7.5	Summary and Analysis of Sliding Dichotomy – Glasgow Outcome Scale – Extended at 6 Months Post Injury – Observed Values (mITT Population)
Appendix 14.2.7.8	Analysis of Glasgow Outcome Scale - Extended at 3 Months Post Injury – Observed Values (mITT Population)
Appendix 14.2.8.2	Analysis of SF-36 by Visit (mITT Population)

Model Checking Figures

Figure 14.2.1.1.1	Graphical Assessment of Proportional Odds Assumption for Proportional Odds Model of Glasgow Outcome Scale at 6 months [Treatment Group] – Missing Values Imputed (mITT Population)
Figure 14.2.1.1.2	Graphical Assessment of Proportional Odds Assumption for Proportional Odds Model of Glasgow Outcome Scale at 6 months [Region] – Missing Values Imputed (mITT Population)
Figure 14.2.1.1.3	Graphical Assessment of Proportional Odds Assumption for Proportional Odds Model of Glasgow Outcome Scale at 6 months [Age] – Missing Values Imputed (mITT Population)
Figure 14.2.1.1.4	Graphical Assessment of Proportional Odds Assumption for Proportional Odds Model of Glasgow Outcome Scale at 6 months [GCS Motor Score] – Missing Values Imputed (mITT Population)
Figure 14.2.1.1.5	Graphical Assessment of Proportional Odds Assumption for Proportional Odds Model of Glasgow Outcome Scale at 6 months [Pupil Response] – Missing Values Imputed (mITT Population)
Figure 14.2.1.1.6	Graphical Assessment of Proportional Odds Assumption for Proportional Odds Model of Glasgow Outcome Scale at 6 months [CT Classification] – Missing Values Imputed (mITT Population)

Figure	14.2.1.1.1
Title 1	Graphical Assessment of Proportional Odds Assumption for Proportional Odds Model of Glasgow Outcome Scale at 6 months – Missing Values Imputed [Treatment Group] (mITT Population)
Title 2	Predictor = Treatment Group
Type of graph	Line graph
y-axis	Empirical Cumulative Logit
y-axis (label)	Empirical Cumulative Logit
x-axis	Treatment Group
x-axis (label)	Treatment Group
Legend (if applicable)	A legend should be included to identify each empirical cumulative logit 1 = EmpLogit ₁ = log[(y ₁)/(y ₂ + y ₃ + y ₄)] , 2 = EmpLogit ₂ = log[(y ₁ + y ₂)/(y ₃ + y ₄)] and 3 = EmpLogit ₃ = log[(y ₁ + y ₂ + y ₃)/(y ₄)] And treatment group: BHR-100 and Placebo
Footnote 1	Program: xxxxxxx.sas, Output: xxxxxxx.rtf, Generated on: DDMONYYYY xx:xx, Page x of x
Additional information	Corresponds to table 14.2.1.1.

Figure	14.2.1.1.2
Title 1	Graphical Assessment of Proportional Odds Assumption for Proportional Odds Model of Glasgow Outcome Scale at 6 months Missing Values Imputed [Region] (mITT Population)
Title 2	Predictor = Region
Type of graph	Line graph
y-axis	Empirical Cumulative Logit
y-axis (label)	Empirical Cumulative Logit
x-axis	Region
x-axis (label)	Region
Legend (if applicable)	A legend should be included to identify each empirical cumulative logit 1 = EmpLogit ₁ = $\log[(y_1)/(y_2+ y_3+ y_4)]$, 2 = EmpLogit ₂ = $\log[(y_1+ y_2)/(y_3+ y_4)]$ and 3 = EmpLogit ₃ = $\log[(y_1+ y_2+ y_3)/(y_4)]$ And region: North America, Europe, Asia and South America
Footnote 1	Program: xxxxxxx.sas, Output: xxxxxxx.rtf, Generated on: DDMONYYYY xx:xx, Page x of x
Additional information	Corresponds to table 14.2.1.1.

Figure	14.2.1.1.3
Title 1	Graphical Assessment of Proportional Odds Assumption for Proportional Odds Model of Glasgow Outcome Scale at 6 months Missing Values Imputed [Age] (mITT Population)
Title 2	Predictor = Age
Type of graph	Line graph
y-axis	Empirical Cumulative Logit
y-axis (label)	Empirical Cumulative Logit
x-axis	Age
x-axis (label)	Age
Legend (if applicable)	A legend should be included to identify each empirical cumulative logit 1 = EmpLogit ₁ = log[(y ₁)/(y ₂ + y ₃ + y ₄)] , 2 = EmpLogit ₂ = log[(y ₁ + y ₂)/(y ₃ + y ₄)] and 3 = EmpLogit ₃ = log[(y ₁ + y ₂ + y ₃)/(y ₄)]
Footnote 1	Program: xxxxxxx.sas, Output: xxxxxxx.rtf, Generated on: DDMONYYYY xx:xx, Page x of x
Additional information	Corresponds to table 14.2.1.1.

Figure	14.2.1.1.4
Title 1	Graphical Assessment of Proportional Odds Assumption for Proportional Odds Model of Glasgow Outcome Scale at 6 months Missing Values Imputed [GCS Motor Score] (mITT Population)
Title 2	Predictor = GCS motor score
Type of graph	Line graph
y-axis	Empirical Cumulative Logit
y-axis (label)	Empirical Cumulative Logit
x-axis	GCS motor score
x-axis (label)	GCS motor score
Legend (if applicable)	A legend should be included to identify each empirical cumulative logit $1 = \text{EmpLogit}_1 = \log[(y_1)/(y_2+ y_3+ y_4)]$, $2 = \text{EmpLogit}_2 = \log[(y_1+ y_2)/(y_3+ y_4)]$ and $3 = \text{EmpLogit}_3 = \log[(y_1+ y_2+ y_3)/(y_4)]$ And GCS motor score: ≤ 2 versus > 2 .
Footnote 1	Program: xxxxxxx.sas, Output: xxxxxxx.rtf, Generated on: DDMONYYYY xx:xx, Page x of x
Additional information	Corresponds to table 14.2.1.1.

Figure	14.2.1.1.5
Title 1	Graphical Assessment of Proportional Odds Assumption for Proportional Odds Model of Glasgow Outcome Scale at 6 months Missing Values Imputed [Pupil Response] (mITT Population)
Title 2	Predictor = Pupil Response
Type of graph	Line graph
y-axis	Empirical Cumulative Logit
y-axis (label)	Empirical Cumulative Logit
x-axis	Pupil Response
x-axis (label)	Pupil Response
Legend (if applicable)	A legend should be included to identify each empirical cumulative logit $1 = \text{EmpLogit}_1 = \log[(y_1)/(y_2+ y_3+ y_4)]$, $2 = \text{EmpLogit}_2 = \log[(y_1+ y_2)/(y_3+ y_4)]$ and $3 = \text{EmpLogit}_3 = \log[(y_1+ y_2+ y_3)/(y_4)]$ And Pupil Response: bilateral, unilateral, no reactive pupils, or not testable
Footnote 1	Program: xxxxxxx.sas, Output: xxxxxxx.rtf, Generated on: DDMONYYYY xx:xx, Page x of x
Additional information	Corresponds to table 14.2.1.1.

Figure	14.2.1.1.6
Title 1	Graphical Assessment of Proportional Odds Assumption for Proportional Odds Model of Glasgow Outcome Scale at 6 months Missing Values Imputed [CT Classification] (mITT Population)
Title 2	Predictor = CT Classification
Type of graph	Line graph
y-axis	Empirical Cumulative Logit
y-axis (label)	Empirical Cumulative Logit
x-axis	CT Classification
x-axis (label)	CT Classification
Legend (if applicable)	A legend should be included to identify each empirical cumulative logit $1 = \text{EmpLogit}_1 = \log[(y_1)/(y_2+ y_3+ y_4)]$, $2 = \text{EmpLogit}_2 = \log[(y_1+ y_2)/(y_3+ y_4)]$ and $3 = \text{EmpLogit}_3 = \log[(y_1+ y_2+ y_3)/(y_4)]$ And CT Classification: Marshall's CT Classification II, III, IV, evacuated and non-evacuated mass lesion
Footnote 1	Program: xxxxxxx.sas, Output: xxxxxxx.rtf, Generated on: DDMONYYYYY xx:xx, Page x of x
Additional information	Corresponds to table 14.2.1.1.

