8. STATISTICAL PLAN

8.1 Sample Size Justification

It is planned to recruit a total of 1180 patients randomized in a 1:1 ratio to BHR-100 or placebo (590 in each treatment group). This sample size estimation is based on the use of a proportional odds model ([Whitehead, 1993](#)) to analyze the primary outcome variable, namely the conventional 5-point GOS at six months after injury. Assuming approximately 31% good outcome, 21% moderate disability, 19% severe disability and 29% combined vegetative state and death, the total sample size of 1180 subjects will give 90% power to detect a common odds ratio of 1.5 of improvement in outcome (i.e. 10% effect size) at the 1% significance level (two-sided). The baseline outcome distribution used is based on the six-month GOS outcome distribution from the head injury population with GCS 3-8 in the previous TBI Phase 3 trials in the International Mission for Prognosis and Analysis of Clinical Trials in TBI Project (IMPACT) Database ([Marmarou et al., 2007](#)).

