4.3 Predetermined Covariates and Prognostic Factors

A number of predetermined prognostic covariates have been defined for consideration within this study:

- Age,
- Motor response component of GCS (1-2, 3, 4, or 5-6) used to determine eligibility,
- Pupillary response (bilateral, unilateral/no reactive pupils/not testable) used to determine eligibility,
- Presence of hypoxia (yes/suspected, no/unknown) any time prior to randomization,
- Presence of hypotension (yes/suspected, no/unknown) any time prior to randomization,
- CT result at baseline (Marshall's CT Classification I/II, III, IV, or evacuated/non-evacuated mass lesion),
- Presence of traumatic subarachnoid hemorrhage (yes, no), and
- Region (North America, Europe, Asia, South America).

All covariates will be measured at baseline, prior to randomization.

Randomization is expected to balance covariates amongst the treatment groups; consequently, no formal testing of baseline comparability will be conducted.

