The fact that the effects of the explanatory variables (e.g. treatment (β_1), etc.) are the same for each model is referred to as the proportional odds assumption and needs to hold for this methodology to be appropriate. This assumption will be tested using the Score Test. A non-significant result (p-value > 0.05) supports the assumption of proportional odds. As the Score Test is known to be anti-conservative, additional graphical methods will be used to assess the proportional odds assumption in greater detail, if the Score Test is statistically significant.

The proportional odds assumption for an ordinal response implies that the curves on the various cumulative logits are parallel. This assumption can be assessed visually for a given predictor (e.g. region) by plotting it against the empirical logits.

For the 4 levels of the GOS there will be 3 cumulative logits which can be expressed as:

$$\begin{aligned} \text{Logit}_1 &= \log[p_1/(1-p_1)] = \log[p_1/(p_2+p_3+p_4)] , \\ \text{Logit}_2 &= \log[(p_1+p_2)/(1-(p_1+p_2))] = \log[(p_1+p_2)/(p_3+p_4)] , \\ \text{Logit}_3 &= \log[(p_1+p_2+p_3)/(1-(p_1+p_2+p_3))] = \log[(p_1+p_2+p_3)/(p_4)] \end{aligned}$$

where $p_i = P(Y=i)$, where Y (response, GOS at 6 months) = i and i=1, 2, 3 or 4.

By using the observed counts, y_i , in the study data empirical logits can be computed for use in plots as follows:

$$\text{EmpLogit}_1 = \log[(y_1)/(y_2+y_3+y_4)]$$

where y_i =number of subjects with Y (response, GOS at 6 months) = i and i=1, 2, 3 or 4.

The empirical logits can then be calculated for each category of the predictor and plotted. If the resulting plotted lines are roughly parallel this can be considered a visual confirmation of the proportional odds assumption.

See Appendix 3 (Model Checking Figures) for plot specification details.

Provided that the proportional odds assumption is not rejected, the POM will then be used to test the null hypothesis that the odds of being “higher” or “lower” on the outcome variable, GOS at 6 months following injury, across the entire range of the outcome, adjusted for region, age, GCS motor score, pupil response, and CT classification (as defined in Section 4.3) is the same in both treatment groups, i.e.

Null Hypothesis:	$H_0 : \beta_1 = 0$
Alternative Hypothesis:	$H_1 : \beta_1 \neq 0$

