In addition to the above POM for the primary analysis, the individual binary logistic regression models will be fitted for each possible dichotomization of the GOS at 6 months, as outlined above under model 1, 2 and 3. This will be done using missing value imputation for the mITT population. This will allow an assessment of the odds ratio for treatment within each possible dichotomization and a further assessment of the proportional odds assumption. If the parameter estimates obtained under each dichotomized model are similar then the proportional odds assumption would seem sensible.

A bar chart illustrating the percentage of responses in each GOS category for each treatment group will be produced for the GOS at 6 months for the mITT (observed values and missing values imputed) and PP populations (observed values).

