Pelvic Fracture (External Fixation)	n (%)	xx (xx.x %)	xx (xx.x %)	xx (xx.x %)
Placement of Chest Tube	n (%)	xx (xx.x %)	xx (xx.x %)	xx (xx.x %)
Placement of Gastric Tube (PEG)	n (%)	xx (xx.x %)	xx (xx.x %)	xx (xx.x %)
Spinal Stabilization/Thoracic	n (%)	xx (xx.x %)	xx (xx.x %)	xx (xx.x %)
Spinal Stabilization/Lumbar	n (%)	xx (xx.x %)	xx (xx.x %)	xx (xx.x %)
Thoracotomy	n (%)	xx (xx.x %)	xx (xx.x %)	xx (xx.x %)
Tracheostomy	n (%)	xx (xx.x %)	xx (xx.x %)	xx (xx.x %)
Urinary Catheter	n (%)	xx (xx.x %)	xx (xx.x %)	xx (xx.x %)
Vascular (Operative)	n (%)	xx (xx.x %)	xx (xx.x %)	xx (xx.x %)
Vascular (Endovascular Treatment)	n (%)	xx (xx.x %)	xx (xx.x %)	xx (xx.x %)
Wound Closure Graft	n (%)	xx (xx.x %)	xx (xx.x %)	xx (xx.x %)
Other	n (%)	xx (xx.x %)	xx (xx.x %)	xx (xx.x %)

Note: Percentages are based on the number of subjects with data in each treatment group and total in the population of interest.

Source: Listing 16.2.4.8.

Program: xxxxxxx.sas, Output: xxxxxxx.rtf, Generated on: DDMONYYYY xx:xx, Page x of x

Table 14.1.4.1 Demographic Characteristics (mITT Population)

Characteristic	Statistic	BHR-100 (N=xx)	Placebo (N=xx)	Total (N=xx)
Age (years)				
	n	xx	xx	xx
	Mean (SD)	xx.x (xx.xx)	xx.x (xx.xx)	xx.x (xx.xx)
	Median	xx.x	xx.x	xx.x
	Q1, Q3	xx.x , xx.x	xx.x , xx.x	xx.x , xx.x
	Min, Max	xx , xx	xx , xx	xx , xx
Sex	N	xx	xx	xx
Male	n (%)	xx (xx.x %)	xx (xx.x %)	xx (xx.x %)
Female	n (%)	xx (xx.x %)	xx (xx.x %)	xx (xx.x %)
Ethnicity	N	xx	xx	xx
Hispanic or Latino	n (%)	xx (xx.x %)	xx (xx.x %)	xx (xx.x %)
Not Hispanic or Latino	n (%)	xx (xx.x %)	xx (xx.x %)	xx (xx.x %)
Not Allowed to Obtain	n (%)	xx (xx.x %)	xx (xx.x %)	xx (xx.x %)
Race	N	xx	xx	xx
White	n (%)	xx (xx.x %)	xx (xx.x %)	xx (xx.x %)
Black, African American or of African heritage	n (%)	xx (xx.x %)	xx (xx.x %)	xx (xx.x %)
Native Hawaiian or other Pacific Islander	n (%)	xx (xx.x %)	xx (xx.x %)	xx (xx.x %)
Asian	n (%)	xx (xx.x %)	xx (xx.x %)	xx (xx.x %)
American Indian or Alaska Native	n (%)	xx (xx.x %)	xx (xx.x %)	xx (xx.x %)
Not Allowed to Obtain	n (%)	xx (xx.x %)	xx (xx.x %)	xx (xx.x %)
Other	n (%)	xx (xx.x %)	xx (xx.x %)	xx (xx.x %)

Note: Percentages are based on the number of subjects with data in each treatment group and total in the population of interest.

Note: Age (years) = (date of informed consent - date of birth + 1)/365.25.

Source: Listing 16.2.4.1.

Program: xxxxxxx.sas, Output: xxxxxxx.rtf, Generated on: DDMONYYYY xx:xx, Page x of x

Table 14.1.4.2 Pregnancy Testing (mITT Population)

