³ The OR and CIs come from a Logistic Regression analysis. The odds of a favorable outcome (GR, MD) will be modeled and will be fitted including treatment, geographic region (North America, Europe, Asia, and South America), age, GCS motor score (1-2, 3, 4, 5-6), pupil response (unilateral, bilateral, no reactive pupils/not testable), and CT classification (I/II, III, IV, V/VI). For factors, the last level is taken as the reference level. For example, CT classification with 4 levels (II-V/VI), level V/VI is taken as the reference level. Marshall CT classification was used.

Source: Listing 16.2.6.1.4 and 16.2.6.1.6.

Program: xxxxxxx.sas, Output: xxxxxxx.rtf, Generated on: DDMONYYYY xx:xx, Page x of x

Table 14.2.3.4 Summary of Dichotomized Glasgow Outcome Scale at 6 Months Post Injury - Observed Values (mITT Population)

Glasgow Outcome Scale ¹	Statistic	BHR-100 (N=xx)	Placebo (N=xx)
n	n	xx	xx
GR, MD	n (%)	xx (xx.x %)	xx (xx.x %)
SD, V/D	n (%)	xx (xx.x %)	xx (xx.x %)

¹ GR=[name]=Moderate Disability, SD=Severe Disability, V/D=Vegetative/Dead. Vegetative state and dead categories are combined.

Note: Percentages are based on the number of subjects in each treatment group in the population of interest.

Source: Listing 16.2.6.1.4.

Program: xxxxxxx.sas, Output: xxxxxxx.rtf, Generated on: DDMONYYYY xx:xx, Page x of x

Note to Programmer: Missing value imputation ONLY done for GR, MD vs. SD, V/D dichotomization.

Table 14.2.3.5 Analysis of Dichotomized (GR, MD vs. SD, V/D) Glasgow Outcome Scale¹ at 6 Months Post Injury - Observed Values (mITT Population)

Table 14.2.3.6 ORs¹ and 95% CIs² for Dichotomized (GR, MD vs. SD, V/D) Glasgow Outcome Scale at 6 Months Post Injury - Observed Values (mITT Population)

Table 14.2.3.7 Summary of Dichotomized Glasgow Outcome Scale at 6 Months Post Injury - Observed Values (PP Population)

Table 14.2.3.8 Analysis of Dichotomized (GR, MD vs. SD, V/D) Glasgow Outcome Scale¹ at 6 Months Post Injury - Observed Values (PP Population)

Table 14.2.3.9 ORs¹ and 95% CIs² for Dichotomized (GR, MD vs. SD, V/D) Glasgow Outcome Scale at 6 Months Post Injury - Observed Values (PP Population)

Table 14.2.3.10 Analysis of Dichotomized (GR vs. MD, SD, V/D) Glasgow Outcome Scale¹ at 6 Months Post Injury - Missing Values Imputed (mITT Population)

Table 14.2.3.11 ORs¹ and 95% CIs² for Dichotomized (GR vs. MD, SD, V/D) Glasgow Outcome Scale at 6 Months Post Injury -Missing Values Imputed (mITT Population)

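### The GCS motor plot used to judge proportional odds collapses the model's four levels to two; the pupil and age plots and the imputation labels for the binary models also need aligning with the primary analysis

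*SAP*

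**What the plan says.** SAP 9.5.1.1 checks proportional odds in three ways.

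- **Score Test** on the primary model, where p > 0.05 supports the assumption. The SAP calls this test anti-conservative.
- **Empirical-logit plots**, used if the Score Test is significant. On their construction the SAP says: "The empirical logits can then be calculated for each category of the predictor and plotted". Roughly parallel lines count as visual confirmation.
- **Three binary logistic models**, one per cut of the GOS, fitted whatever the Score Test shows. On their data the SAP says: "This will be done using missing value imputation for the mITT population".

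If the assumption cannot be justified, the sliding dichotomy becomes the primary analysis (SAP 9.5.1.2).

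SAP 4.3 defines the motor covariate as "Motor response component of GCS (1-2, 3, 4, or 5-6) used to determine eligibility", and the footnote to Table 14.2.1.2 repeats those four levels. The legend of Figure 14.2.1.1.4 (SAP Appendix 2, Model Checking Figures) reads "And GCS motor score: ≤ 2 versus > 2".

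The programmer note under Table 14.2.3.4 (SAP Appendix 3) says: "Missing value imputation ONLY done for GR, MD vs. SD, V/D dichotomization". In Appendix 2, the statistical output Appendix 14.2.3.12 carries the label *Observed Values*, while the tables it supports are titled as imputed.

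**The concern.** Once the Score Test is significant, the plots become evidence for or against keeping the proportional odds model as primary. No numerical rule for parallelism is given, so the way each plot is specified largely determines what the reader can see. A plot that pools levels the model keeps apart can hide a violation inside the pooled group. It can also show a slight drift when the model holds exactly.

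The binary models serve as a check because their treatment estimates should agree when proportional odds holds. That comparison is clean only if all three are fitted to the same patients. An instruction that imputes for one cut but not for the others would add differences unrelated to proportionality.

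**Working it through.** **1. The plan's own figure.** Protocol 8.1 states that "1180 subjects will give 90% power to detect a common odds ratio of 1.5 of improvement in outcome" at a two-sided 1% level, with placebo shares of 31/21/19/29%. The Whitehead formula is N = 12(z₁ + z₂)² / [(ln OR)²(1 − Σp̄³)]. An odds ratio of 1.5 gives average shares across arms of 0.356, 0.213, 0.178 and 0.252, so Σp̄³ = 0.0766. Then N = 12 × (2.576 + 1.282)² / (0.4055² × 0.9234) ≈ 1176, which agrees with 1180. Nothing below alters this figure.

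**2. The Score Test.** With the SAP 4.3 coding the model has 1 (treatment) + 3 (region) + 1 (age) + 3 (motor) + 1 (pupils) + 3 (CT) = 12 slopes. With three cuts the test has 12 × 2 = 24 df, or 26 if pupils have three levels. It uses the model's own coding and data.

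**3. The six plots against the model.** All six are titled as imputed mITT data, as the primary model is.

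| Predictor | Primary model | Plot | Match |
|---|---|---|---|
| Treatment | 2 arms | 2 arms | yes |
| Region | 4 | 4 | yes |
| Motor | 1-2, 3, 4, 5-6 | ≤2, >2 | no, coarser |
| Pupils | 2 levels (SAP 4.3 and the rows of Table 14.2.1.3); 3 in the footnotes | 4 | no, finer |
| CT | I/II, III, IV, mass lesions pooled | II, III, IV, evacuated and non-evacuated mass lesion | unclear whether pooled |
| Age | single covariate | no bands named | not drawable until banded |

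**4. What the motor collapse can do.** The inputs here are assumptions, not taken from the documents: motor shares 30/15/25/30%, and level 1-2 logits of −1.2, −0.3 and 0.8 for good recovery, moderate disability or better, and severe disability or better. The pooled >2 probability is (15p₃ + 25p₄ + 30p₅₋₆)/70. The plotted odds ratio is exp[logit(pooled) − logit(level 1-2)].

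*(a) Proportional odds violated on four levels.* Odds ratios against level 1-2 are given at the three cuts, with the resulting probability in brackets.

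| Level | Good recovery | Moderate or better | Severe or better |
|---|---|---|---|
| 3 | 2.46 (0.426) | 1.49 (0.525) | 0.90 (0.668) |
| 4 | 2.01 (0.378) | 2.01 (0.599) | 2.01 (0.818) |
| 5-6 | 2.30 (0.409) | 3.02 (0.691) | 5.62 (0.926) |
| Pooled >2 | 0.401, logit −0.4 | 0.622, logit 0.5 | 0.832, logit 1.6 |
| Plotted OR | e^0.8 = 2.23 | e^0.8 = 2.23 | e^0.8 = 2.23 |

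The case was solved so that the two-level plot is exactly parallel. It shows that a violation can be hidden completely, not that hiding is typical.

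*(b) Proportional odds exact on four levels*, with odds ratios 1.65, 2.72 and 6.05 at every cut. The two-level plot gives 3.44, 3.26 and 3.11, a small artefact.

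**5. The binary models.** Stating imputed data: SAP 9.5.1.1, the titles of Tables 14.2.3.10 to 14.2.3.13 in Appendices 2 and 3, and the title of Appendix 14.2.3.10. Against: the note under Table 14.2.3.4, read literally, and the title of Appendix 14.2.3.12.

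Size if the note were followed: the unadjusted SE of a log odds ratio at the middle cut (placebo 52%) is √[4/(1180 × 0.52 × 0.48)] ≈ 0.12. If a fraction f of outcomes is imputed, fitting on different records adds noise of about SE × √f. For an assumed f of 5% to 10% that is 0.12 × √0.05 ≈ 0.027 to 0.12 × √0.10 ≈ 0.038.

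**The case against.** The strongest reply is that the checks are mostly sound and what remains is figure clean-up. Much of that stands.

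- A reader might infer that the checks as a whole cannot test proportional odds. They can. The Score Test is the gate and runs on the primary model, and the treatment plot, which bears directly on the effect under test, matches it.
- A reader might infer that the plots use different data. They do not; all six use the imputed mITT population.
- A reader might say that the motor plot shows one of the model's three contrasts. It shows a pooled average of all three, so none is shown separately.
- A reader might note that age is derived as "Age (years) = (date of informed consent - date of birth + 1)/365.25" and conclude that almost every plotted point would be one patient with an infinite logit. SAP 9.5.1.1 calls for logits by category, so plotting exact ages would contradict the stated method. The real gap is that this figure's bands are not named.
- The pupil plot is finer than the model and hides nothing. However, Protocol 4.1 requires at least one reactive pupil, so a separate level with no reactive pupils should be nearly empty.
- The CT legend can be read as one pooled mass-lesion level. Leaving out class I fits Protocol 8.4.6, which expects no such patients.
- The note under Table 14.2.3.4 sits beneath an observed-values shell that shows only the middle cut, and may be a mis-worded statement about that shell. No observed-value tables for the outer cuts are listed, so a comparison of one imputed estimate with two observed-case estimates is not a planned output.
- The SAP expects minimal missing data, and Protocol 8.3.1 runs the sliding dichotomy as a sensitivity analysis in any event, so both results will be available.

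None of this answers the motor plot, which is coarser than the model it is meant to check, or removes the contradictory imputation instructions.

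**Conclusion.** The point holds in limited form. The motor plot cannot show non-proportionality among levels 3, 4 and 5-6, and it feeds a by-eye judgement that can change the primary analysis. The pupil coding is inconsistent (two, three or four levels depending on the place), the age bands are unnamed, and the imputation instructions for the outer-cut binary models conflict.

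The consequence arises only if the Score Test is significant, apart from the binary models, which are always fitted. The size of the motor problem cannot be derived from the documents; the illustration rests on assumed shares and logits and shows only what is possible. The binary-model noise, about 0.03 to 0.04 on the log odds ratio against an SE of about 0.12, is small and rests on an assumed 5% to 10% of outcomes imputed. Power, alpha and sample size are unaffected.

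**What to change.** 1. Redraw Figure 14.2.1.1.4 on motor levels 1-2, 3, 4 and 5-6.
2. Settle whether the model has two or three pupil levels, reconciling SAP 4.3 with the footnotes to Tables 14.2.1.2 and 14.2.1.3, and use the same levels in Figure 14.2.1.1.5.
3. State in Figure 14.2.1.1.6 that evacuated and non-evacuated mass lesions are pooled.
4. Name the age bands for Figure 14.2.1.1.3 before unblinding.
5. Fit all three binary models on the same imputed mITT data, as SAP 9.5.1.1 states. Correct the note under Table 14.2.3.4 and the title of Appendix 14.2.3.12.

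The cost is a few edits to figure specifications, one note and one title, with no new data. Timing matters: choosing levels or bands after unblinding would be a post hoc input to the choice of primary analysis.
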